2.9 Sample size justification

We expect a 90-day mortality of 40% in the standard arm. This mortality rate is compatible with 90-day mortality reported in contemporary cohorts of patients with RRT-requiring AKI in Finland and Australia/New Zealand.^{4,21} There is no clear guidance on the estimated risk reduction afforded by accelerated RRT so we have selected a relative risk reduction of 15% (absolute risk reduction 6%) as recommended by experts to be an effect magnitude that is minimally important and conceivable with this intervention.⁴⁹ With Type I error of 0.05 and power of 0.90, a sample size of 1,359 patients/arm would be required (total 2,718). In order to account for the interim analyses, the required sample size increases to 2,780. After accounting for a combined rate of crossover and dropouts of 3% (as derived from the pilot phase), we will target a total sample size of 2,866.

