2.10 Analysis plan

Baseline data will be summarized descriptively. The primary outcome of 90-day mortality will be evaluated using an intent-to-treat approach. A simple comparison of proportions will be performed using a chi-squared test. The risk ratio and relative risk reduction will be estimated with 95% confidence intervals. An adjusted analysis will also be completed using logistic regression and will include the following baseline variables: age, sex, sepsis, receipt of cardiopulmonary bypass and SOFA score.

The principal secondary outcome, the proportion of survivors who are RRT dependent at 90 days, presents challenges as the non-inclusion of participants who died might obviate the inter-group balance afforded by randomization. We will consider two complementary approaches to examine this question. First, we will use the adjusted model for the primary outcome to estimate the probabilities of 90-day survival. We will then use the reciprocals of these as weights in a logistic regression for RRT, resulting in an inverse probability weighted analysis. This is typically called a marginal structural model. The second approach will employ a multinomial regression model to jointly consider the states: dead at 90 days, alive at 90 days receiving RRT and alive at 90 days RRT-free. A similar approach will be used to estimate the probabilities of 365-day survival and to consider the states: dead at 365 days, alive at 365 days receiving RRT and alive at 365 days RRT-free.

Duration of ventilation, vasoactive therapy, ICU stay and hospitalization and albuminuria at 90 days (expressed as the urinary albumin to creatinine ratio in mg/mmol) will be compared by means of a t-test. Finally, eGFR decline of 25%, death in ICU, by 28 days and in-hospital, and ICU readmission and rehospitalization within 90 days will be compared by chi-squared tests.

Interim analyses for efficacy based on the primary outcome will be done when 25, 50 and 75% of planned enrollees have completed 90-day follow-up. Given the risks of false positive results with early stopping for benefit, statistical significance will be declared using small p-values established by O'Brien-Fleming boundaries on the primary outcome (90-day mortality). A detailed monitoring plan will be developed in consultation with the DSMB prior to commencement of recruitment.

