The STARRT-AKI trial population will include a minimum of 2866 patients, in order to have at least 90% power to detect a 15% relative reduction (6% absolute risk reduction) in the risk of death, assuming an estimated baseline 90-day all-cause mortality of 40%. The baseline mortality rate was based on the available published literature and data from our pilot trial.^{14,15} A 15% relative risk reduction required a total sample of 2718 (1359 patients per arm); however, to account for the three planned interim analyses and an estimated combined rate of crossover, dropout and loss to follow-up of 3%, the total sample size was increased to include a minimum of 2866 patients. Following the planned third interim analysis, performed when 75% of recruitment had been achieved (24 April 2019), the Data Safety Monitoring Board (DSMB) supported the extension of recruitment to achieve a sample size of a minimum of 3000 patients.

Statistical analysis

Analysis principles

Analysis will be performed on an intention-to-treat (ITT) basis. ● All tests will be two-sided and the overall type I error probability for the primary outcome will not exceed 5% ($\alpha = 0.05$) over the three interim analyses by employing an O'Brien—Fleming stopping boundary. This approach gives P values thresholds for stopping at each of the interim analyses of 0.00001473, 0.003045 and 0.0183, respectively, and a required significance level of 0.044 at the final analysis.¹⁶ The primary outcome will be analysed independently by two statisticians. For secondary analyses and endpoints, P values will be reported, but since these are best viewed as exploratory, formal hypothesis testing (ie, for rejection of null hypotheses) will be avoided. ● This SAP and the main STARRT-AKI trial manuscript will only include analyses up to 90 days after randomisation. ● The analysis of one-year outcomes (eg, mortality, dialysis dependence, health-related quality of life) and health economic outcomes will be reported separately and the analytic approach to these outcomes will not be covered in this SAP.

- Pre-specified subgroup analyses will be performed irrespective of the result for the primary outcome.
- Secondary outcome analyses will be performed irrespective of the result for the primary outcome and will be considered exploratory.

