- The secondary analyses will not be adjusted for multiple testing; however, the results of all statistical testing will be reported according to the American Statistical Association guidelines to provide the necessary context for interpretation.¹⁷
- All estimates of treatment effect will be accompanied by 95% confidence intervals (CI).
- All analyses will be performed using the R software package (R Core Team, 2008; www.R-project.org).

Interim analyses and the Data Safety Monitoring Board

An independent DSMB will review unblinded data to examine recruitment rate, patient characteristics, randomisation compliance, treatment compliance, completeness of data, outcomes and adverse events on three occasions (following the completion of 90-day follow-up for the 716th, 1432nd and 2150th patient, respectively). The DSMB charter is available at: <https://www.ualberta.ca/critical-care/research/current-research/starrtaki/documents.10>

Analysed datasets

All main analyses will be performed on the ITT population dataset. For these analyses, all patients will be analysed according to the group to which they were randomised; however, any randomised patient found to have not fulfilled eligibility criteria based on data available at the time of initial assessment (ie, randomised in

error) will be excluded following independent adjudication by two investigators who will be blinded to outcomes.¹⁸

Trial profile

The flow of patients through the trial will be shown in a Consolidated Standards of Reporting Trials (CONSORT) diagram (Figure 1).¹⁹ The figure will provide a summary of the number of patients screened, the number of patients who fulfilled eligibility, the number of patients who were excluded and the reason(s) for exclusion.

Patient characteristics and baseline comparisons

- A description of baseline characteristics will be presented by treatment allocation, as outlined in the proposed Table 1 .
- Categorical variables will be summarised with frequencies and percentages. Percentages will be calculated according to the number of patients for whom data are available.

- Continuous variables will be summarised as means with standard deviation (SD) or medians with the interquartile range (IQR) (Q1 and Q3).

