Evaluation of heterogeneity in treatment effect Death at 90 days will also be analysed across baseline predicted risk of death using the SAPS II score ²¹ This analysis will be assessed by adding an interaction between treatment and SAPS II in the fully adjusted model described earlier.

Subgroup analyses

We will evaluate the effect of allocated treatment on the primary outcome across the following a priori defined subgroups by means of interaction terms in the adjusted model and displayed in a forest plot: ● patient sex; ● baseline eGFR, ● baseline SAPS II score; ● primary reason for ICU admission surgical versus medical; ● sepsis; and ● geographic region (eg, North America, Europe, Australia/ New Zealand, Asia/South America etc).

Exploratory analyses of the primary outcome We will further evaluate the primary outcome with the following exploratory analyses:

- We will examine the effect of the allocated treatment on the primary endpoint in a per-protocol population, defined by omitting patients with a protocol violation due to crossover to the opposite allocated treatment to which they were randomised.

- We will examine the effect of the treatment on the primary endpoint in a modified ITT (mITT) population. The mITT population will be defined as an "as treated" population, whereby patients with a protocol violation will be analysed in the treatment arm that reflects the RRT initiation strategy that was received.
- To further inform the interpretability of the main primary analysis, we will examine the utility of a Bayesian analysis approach, across a range of plausible reference and data-driven priors, to provide estimates of the posterior probability of any mortality benefit (using both relative risk and absolute risk reduction), of an accelerated compared with standard strategy for RRT initiation in critically ill patients with severe AKI ²²
These proposed exploratory analyses may be reported after the publication of the main trial findings.

Additional analyses of mortality

The analysis of all-cause mortality described in the main analysis will be replicated to compare the proportion of patients who died in the ICU, before hospital discharge, and at 28 days after randomisation, respectively. No additional adjusted or subgroup analyses will be performed on these endpoints.

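### The 3% allowance that takes 2,780 to 2,866 includes crossover but is applied wholly as loss from analysis, so the 90% power claim at 2,866 rests on an unstated assumption (minor)

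*Protocol*

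**What the plan says.** Protocol section 2.9 assumes 40% mortality at 90 days in the standard arm and a 15% relative (6-point absolute) reduction, described as "an effect magnitude that is minimally important and conceivable with this intervention". It obtains 1,359 per arm (2,718 in total), raises this to 2,780 for the interim analyses, and then takes a last step: "After accounting for a combined rate of crossover and dropouts of 3% (as derived from the pilot phase", giving 2,866.

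The SAP (Sample size) keeps the figure but widens what it covers, to "an estimated combined rate of crossover, dropout and loss to follow-up of 3" per cent. It says the minimum of 2,866 was set "in order to have at least 90% power to detect a 15% relative reduction (6% absolute risk reduction) in the risk of death". It also records that after the third interim analysis the DSMB "supported the extension of recruitment to achieve a sample size of a minimum of 3000 patients". It does not link that extension to crossover.

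On the analysis set, Protocol section 2.10 says: "The primary outcome of 90-day mortality will be evaluated using an intent-to-treat approach". The SAP (Analysed datasets) says that "all patients will be analysed according to the group to which they were randomised". Crossovers are removed only in the exploratory per-protocol population, "defined by omitting patients with a protocol violation due to crossover to the opposite allocated treatment to which they were randomised".

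Neither document divides the 3% between crossover and loss, says whether it is a share of all patients or the sum of the two arm rates, or mentions dilution of the effect.

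**The concern.** Loss and crossover act on power in different ways. A patient without an outcome leaves the analysis, and dividing N by (1 − d) restores the planned number. A patient who crosses over stays in the intention-to-treat comparison. N is unchanged, but the expected difference may shrink by a factor (1 − c), and making that good needs N/(1 − c)². The plan applies the first correction to a rate that, by its own description, includes the second kind of event.

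What is at stake is the accuracy of a stated power. The design, the analysis and the primary test are unaffected. The power statement matters most if the result is null, because Protocol section 1.1 says that absence of superiority would justify the conservative strategy. A reader weighing a null result needs to know what power was really claimed, and under what adherence.

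**Working it through.** **Inputs.** From the protocol: 40% v 34%, two-sided 0.05, 90% power, 1:1 allocation, 2,780, 3%, 2,866. From the SAP: P-value thresholds 0.00001473, 0.003045, 0.0183 and 0.044, taken at 25, 50, 75 and 100% of information. From the pilot (Protocol sections 1.5.4 and 2.14): 3/48 late starts in the accelerated arm, no starts within 12 hours among 52 in the standard arm, and complete Day-90 follow-up.

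**The plan's own figures.**
- Fixed design: (1.960·√(2·0.37·0.63) + 1.2816·√(0.40·0.60 + 0.34·0.66))² / 0.06² = 1,358.6, so 1,359 per arm and 2,718 in total. This reproduces.
- Interim step: numerical integration of the four SAP thresholds gives type I error 0.0500 and an inflation of 1.018, hence about 2,768. The stated 2,780 is within 0.5%.
- Last step: 2,780/0.97 = 2,865.98, so 2,866. This is exactly the loss formula with d = 3%.

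**Power with crossover treated as dilution.** Let d be the proportion lost, and let cA and cS be the proportions crossing over in each arm multiplied by the share of effect they lose. Then analysed n = N(1 − d) and the difference = 6 × (1 − cA − cS) points. Power is group-sequential with the SAP thresholds and pooled variance; unpooled variance adds about 0.1 point throughout.

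| Assumption | Difference | Power at 2,866 | Power at 3,000 |
|---|---|---|---|
| All 3% is loss | 6.00 | 90.1% | 91.3% |
| Pilot late-start rate (6.25% of accelerated arm), a quarter of effect lost | 5.91 | 90.1% | 91.3% |
| 1.5% loss; arm crossover rates sum to 1.5% | 5.91 | 89.7% | 90.9% |
| No loss; arm crossover rates sum to 3% | 5.82 | 89.2% | 90.5% |
| Pilot late-start rate, half of effect lost | 5.81 | 89.1% | 90.4% |
| 1.5% loss; 1.5% crossover in each arm | 5.82 | 88.8% | 90.1% |
| 1% loss; 2% crossover in each arm | 5.76 | 88.3% | 89.6% |
| Worst case: 3% crossover in each arm, all effect lost | 5.64 | 87.3% | 88.7% |
| Worst case: pilot late-start rate, all effect lost | 5.625 | 87.0% | 88.5% |

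**Break-even.** With no loss at all, power at 2,866 falls to 90% once the difference is diluted by about 1.6%. At the pilot rate that is 1.6/6.25, or about a quarter of the effect in late starters. At 3,000 the break-even dilution is about 3.8%.

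**Two meanings of 3%.** If it is the sum of the arm rates, full dilution multiplies the difference by 0.97, and 2,780/0.97² = 2,955. If it is 3% of all patients, that means 3% of each arm, and the factor is 0.94: 2,780/0.94² = 3,147. The two readings fall on opposite sides of 3,000.

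**What the pilot suggests.** 3/48 and 0/52 together are 3/100 = 3%, and follow-up was complete. That fits a 3% made up mainly of crossover, counted over all patients. It is an inference: the protocol says the rate came from the pilot but not how.

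**The case against.** The strongest reply is that no figure is wrong. The 6 points was chosen as a minimally important difference, not estimated in full adherers, and the trial compares randomised strategies. The protocol lets clinicians start RRT in the standard arm on their own judgment and expects some crossover whatever is done. A target difference between such strategies may already include non-adherence, and then nothing further is lost. This stands as a possible reading. Against it, a separate allowance for crossover would then be unnecessary, and no passage says the difference is net.

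A second reply is that a late accelerated start is not the standard strategy. Protocol section 2.4 has staff keep pressing for RRT after 12 hours, whereas pilot standard-arm patients who started did so at a median of 31.6 hours. This also stands. It is why full loss of effect is only a worst case, and why losing up to about a quarter leaves the claim intact. The half-loss and mixed rows are assumptions, not figures from the documents. The mixed rows also include some loss, and those with crossover in both arms include standard-arm crossover; the pilot text reports neither.

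Third, the shortfall is about one point on these rows, and the extension to 3,000 largely absorbs it. That is true, but the SAP still attaches its claim to 2,866 without qualification.

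Two stronger inferences should be resisted. A reader might conclude that 2,866 is a miscalculation or that the trial is underpowered; the figures reproduce and the shortfall is conditional. A reader might equally conclude from 2,955 being below 3,000 that the extension settles the matter even if the whole 3% is dilution. That holds only if the 3% is the sum of the arm rates. If it is 3% of all patients with full loss of effect, power at 3,000 is about 88.5%.

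**Conclusion.** The point holds as a minor, conditional one. The loss formula was applied to a rate that includes crossover, and the unqualified power claim at 2,866 needs one of three conditions: essentially all loss, at most about a quarter of the effect lost at the pilot late-start rate, or a 6-point difference already net of crossover. Without one of them, power at 2,866 is about 89% on the even-split and half-loss rows (88.8% to 89.7%), with a more crossover-heavy mix at 88.3%, and about 87% at full dilution. At 3,000 the corresponding figures are about 90% to 91% (89.6% for the crossover-heavy mix) and about 88.5%.

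These results take 40% v 34% and the SAP thresholds as given. The split of the 3%, its base and the share of effect lost are assumptions shown as a range. The documents do not support a claim that more patients must be enrolled, or that 3,000 secures 90% under every reading.

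**What to change.** In Protocol section 2.9 and the SAP's Sample size section:

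1. Divide the 3% into loss to follow-up, which inflates N, and crossover, which dilutes the difference.
2. Say whether the crossover rate is a share of all patients or the sum of the arm rates.
3. Say whether the 6 points is already net of non-adherence; if it is, assign the 3% to loss only.
4. Restate power at 2,866 and at 3,000 under the chosen assumption, with full dilution (about 87% and 88.5%) given as a labelled worst case.

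The cost is wording. The stated power at 2,866 may become slightly less favourable. The remedy is to restate the figure, not to enrol more, and the design and the primary analysis stay as they are.

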2.10 Analysis plan

Baseline data will be summarized descriptively. The primary outcome of 90-day mortality will be evaluated using an intent-to-treat approach. A simple comparison of proportions will be performed using a chi-squared test. The risk ratio and relative risk reduction will be estimated with 95% confidence intervals. An adjusted analysis will also be completed using logistic regression and will include the following baseline variables: age, sex, sepsis, receipt of cardiopulmonary bypass and SOFA score.

The principal secondary outcome, the proportion of survivors who are RRT dependent at 90 days, presents challenges as the non-inclusion of participants who died might obviate the inter-group balance afforded by randomization. We will consider two complementary approaches to examine this question. First, we will use the adjusted model for the primary outcome to estimate the probabilities of 90-day survival. We will then use the reciprocals of these as weights in a logistic regression for RRT, resulting in an inverse probability weighted analysis. This is typically called a marginal structural model. The second approach will employ a multinomial regression model to jointly consider the states: dead at 90 days, alive at 90 days receiving RRT and alive at 90 days RRT-free. A similar approach will be used to estimate the probabilities of 365-day survival and to consider the states: dead at 365 days, alive at 365 days receiving RRT and alive at 365 days RRT-free.

Duration of ventilation, vasoactive therapy, ICU stay and hospitalization and albuminuria at 90 days (expressed as the urinary albumin to creatinine ratio in mg/mmol) will be compared by means of a t-test. Finally, eGFR decline of 25%, death in ICU, by 28 days and in-hospital, and ICU readmission and rehospitalization within 90 days will be compared by chi-squared tests.

Interim analyses for efficacy based on the primary outcome will be done when 25, 50 and 75% of planned enrollees have completed 90-day follow-up. Given the risks of false positive results with early stopping for benefit, statistical significance will be declared using small p-values established by O'Brien-Fleming boundaries on the primary outcome (90-day mortality). A detailed monitoring plan will be developed in consultation with the DSMB prior to commencement of recruitment.

We will evaluate the effect of accelerated vs. standard RRT in the following *a priori* defined subgroups: i) patients with sepsis (based on the possibility that earlier RRT, due to more aggressive removal of inflammatory mediators, might have a more prominent effect among patients with sepsis-associated AKI); ii) patients whose baseline eGFR is < 45 mL/min/1.73 m² (based on the possible modifying effect of pre-existing chronic kidney disease on mortality and progression to chronic RRT dependence) and iii) region of the world- Canada/US vs Australia/NZ vs Europe (based on possibility that regional RRT and/or critical care practices have a modifying effect on the impact of the intervention on outcomes).

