The proportion of survivors who are RRT-dependent at 90 days requires special consideration, as the non-inclusion of participants who died might obviate the intergroup balance afforded by randomisation. We will undertake two complementary approaches. First, we will develop a model for the primary outcome to estimate the probabilities of 90-day survival.

We will then use the reciprocals of these probabilities as weights in a logistic regression for RRT dependence, resulting in an inverse probability weighted analysis. The second approach will employ a multinomial regression model to jointly consider the following states: dead at 90 days, alive at 90 days receiving RRT, and alive at 90 days free of RRT. In addition, time-to-event models that incorporate competing risks or multiple outcomes will be considered.

Days alive and free of outcome will be calculated for treatment with RRT through 90 days, vasoactive therapy through 28 days, mechanical ventilation through 28 days, ICU stay through 28 days, and hospital stay from randomisation through 90 days (Table 2). These will be summarised by treatment allocation using means (SDs) or medians (IQRs). Differences will be explored using linear regression and presented as a mean difference (95% CI).

We will obtain a measure of health-related quality of life at 90 days using the EuroQoL EQ-5D-5L scale to enable a cost-effectiveness analysis of the two approaches to RRT initiation ¹² This health economic evaluation will be reported after the publication of the main trial findings.

Analyses of adverse events and serious adverse events

The number and percentage of adverse events and serious adverse events occurring between randomisation and 14 days will be reported for the treatment arm (Table 3).

References

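### The survival weights for RRT dependence among survivors should come from arm-specific death models that include kidney function; main-effects weights leave most of the survivor imbalance in place if the mortality effect varies

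*Protocol*

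**What the plan says.** Protocol section 2.10 recognises that, in a comparison of survivors, "the non-inclusion of participants who died might obviate the inter-group balance afforded by randomization". It offers two complementary remedies. The first is weighting: "First, we will use the adjusted model for the primary outcome to estimate the probabilities of 90-day survival", and then "We will then use the reciprocals of these as weights in a logistic regression for RRT". The adjusted model in question is a logistic regression on "age, sex, sepsis, receipt of cardiopulmonary bypass and SOFA score". No eGFR or creatinine term is listed and no treatment interaction is stated. The second remedy is a multinomial model for dead, alive on RRT, and alive without RRT.

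The same section justifies a subgroup with baseline eGFR below 45 by the "possible modifying effect of pre-existing chronic kidney disease on mortality and progression to chronic RRT dependence".

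The SAP, under Analysis of other secondary outcomes, loosens the link to the adjusted model: "First, we will develop a model for the primary outcome to estimate the probabilities of 90-day survival". It gives no covariates and no interactions for that model. The one adjusted death model it specifies (Adjusted sensitivity analysis) names, as examples, baseline eGFR, SAPS II, sepsis, surgical status, age and sex, with splines for the continuous variables. Treatment interactions with eGFR, sepsis, SAPS II, region and other factors appear under Subgroup analyses and Evaluation of heterogeneity, for mortality only.

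**The concern.** Randomisation balances the arms at entry. Survivors of the two arms then differ on a baseline variable only if the ratio of survival between arms differs across levels of that variable. If the variable also predicts RRT dependence, the survivors-only comparison is biased. Weighting by the reciprocal of survival probability removes the bias only if the survival model captures how survival depends on arm and that variable together.

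A main-effects logistic model gives every patient the same treatment odds ratio, so it repairs only the imbalance that a constant odds ratio implies. A model without kidney function cannot repair imbalance in kidney function, except through correlation with the listed variables. The protocol itself names CKD as a possible modifier of both death and dependence, which are the conditions that create this bias. At stake is the outcome that Protocol section 1.2 calls the principal secondary outcome. A difference in it also triggers the economic extrapolation in section 2.8.

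**Working it through.** **Plan's own figures.** The documents give no figure for the weighted analysis. The mortality inputs, 40% v 34%, come from Protocol section 2.9. With two-sided alpha 0.05 and power 0.90, n per arm = [1.960 x sqrt(2 x 0.37 x 0.63) + 1.2816 x sqrt(0.40 x 0.60 + 0.34 x 0.66)]^2 / 0.06^2 = 1,358.6, so 1,359 per arm, and 2,780/0.97 = 2,866. Both match. The sample size does not depend on this point.

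**Assumed inputs, not in the documents.** CKD in 25%; RRT dependence 20% with CKD and 5% without; CKD independent of the other model covariates. For the sepsis case: 60% septic, dependence 10% v 5%. Treatment has no effect on dependence, so the true OR is 1.00.

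**Formulas.** For each arm, the weighted share of CKD among survivors is

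s = p(1 - m1)w1 / [p(1 - m1)w1 + (1 - p)(1 - m0)w0],

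where p is the prevalence, m1 and m0 are true mortality with and without CKD, and w = 1/(1 - fitted mortality). Dependence is 0.05 + 0.15s, and the OR compares the arms.

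**One scenario in full: larger benefit in CKD.** Mortality is 46% (CKD) and 38% (no CKD) in the standard arm, overall 0.25 x 0.46 + 0.75 x 0.38 = 0.40. It is 34% in both groups in the accelerated arm.

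- Crude: s = 0.135/0.60 = 0.225 (standard) and 0.165/0.66 = 0.250 (accelerated). Dependence is 8.375% and 8.750%. OR = (0.0875/0.9125)/(0.08375/0.91625) = 1.049.
- Weights without eGFR: under the independence assumption they carry no information on CKD, so the OR stays 1.049.
- Main-effects weights with eGFR: the fitted mortalities (no CKD, CKD) are 0.390 and 0.431 (standard), 0.330 and 0.369 (accelerated). Then s = 0.237 and 0.261, and OR = 1.046.
- Arm-specific weights: s = 0.250 in both arms, OR = 1.000.

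**All scenarios.** Entries are ORs. Mortality is shown as standard to accelerated.

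| Scenario | Mortality, factor present | Mortality, factor absent | Crude | Weights without eGFR | Main effects, factor included | Arm-specific |
|---|---|---|---|---|---|---|
| Larger benefit in CKD | 46% to 34% | 38% to 34% | 1.049 | 1.049 | 1.046 | 1.000 |
| Benefit only in CKD | 46% to 22% | 38% to 38% | 1.139 | 1.139 | 1.142 | 1.000 |
| Benefit only without CKD | 46% to 46% | 38% to 30% | 0.960 | 0.960 | 0.948 | 1.000 |
| Benefit only in sepsis | 44% to 34% | 34% to 34% | 1.028 | n/a (sepsis is listed) | 1.025 | 1.000 |

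**Scale.** With 3,000 patients there are about 900 and 990 survivors. At 8.5% dependence, SE(log OR) = sqrt[1/(900 x 0.085 x 0.915) + 1/(990 x 0.085 x 0.915)] = 0.165. Residual bias under main-effects weights, |ln OR|/0.165, is 0.27, 0.80, 0.32 and 0.15 SE in table order.

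**Second set-up, wider assumptions.** Poor kidney function in 20-30%, its odds ratio for death 1.5-3 and for dependence 3-6, overall dependence 10%, plus a separate severity factor with a death odds ratio of 3. Weights of the protocol type use arm and severity.

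| Treatment effect on death | Unweighted | Protocol-type weights | Kidney function added, no interaction | With interaction |
|---|---|---|---|---|
| Constant odds ratio | 1.005-1.026 | 1.005-1.028 | 1.000 | 1.000 |
| Kidney death OR x 0.67 under accelerated RRT | 1.034-1.090 | 1.036-1.096 | 1.035-1.077 | 1.000 |
| Kidney death OR x 0.5 under accelerated RRT | 1.054-1.138 | 1.058-1.147 | 1.058-1.133 | 1.000 |

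Here the SE is about 0.16. Adding kidney function alone is enough only in the first row.

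**The case against.** The strongest reply is that the SAP has moved on. A reader of the protocol might infer that the current weights omit kidney function. The documents do not support that: the SAP leaves the weight model open, and its adjusted death model already names baseline eGFR. Nor can it be said that interactions are excluded; the SAP neither includes nor rules them out. This objection stands. It narrows the point to what the SAP should specify, but it does not remove it: the protocol's list is the only one given for the weights, and neither specified death model would be enough under effect modification.

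A reader might also infer that the weights enlarge the bias while being presented as corrected. Main-effects weights increase it slightly in two of the four scenarios and reduce it slightly in the other two. The SAP reports the unadjusted relative risk and risk difference as well, and calls secondary analyses exploratory.

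The largest figure needs CKD mortality to fall from 46% to 22%, against a trial target of 6 points overall. The equality of crude and protocol-weighted results follows from assuming CKD independent of the listed covariates, which is the worst case. The documents do not give the components of SOFA, so whether it carries some kidney information is left open.

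Finally, the weights are one of two approaches. The multinomial model and the death-or-dependence composite do not use them, and the SAP will consider competing-risk models. That limits the stakes. But no covariates are stated for the multinomial model; with treatment alone, its contrast between the two surviving states equals the crude odds ratio. The composite answers a different question.

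**Conclusion.** The point holds as a worthwhile, inexpensive improvement. The documents specify main-effects death models only, and weights from such a model leave most of the survivor imbalance in place when the mortality effect varies with kidney function or sepsis.

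Under the assumed inputs, residual bias in the OR is about 2-5% (0.15-0.3 SE) in the three moderate cell scenarios and about 14% (0.8 SE) only with CKD mortality halved. The second set-up gives about 4-8% for the milder interaction. It reaches about 13% with kidney function in the model only when a halved kidney odds ratio for death is combined with a strong link to dependence. With a constant odds ratio and eGFR in the model, the bias is near zero.

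None of these prevalences, dependence risks or interactions is in the documents, so the figures show scale and are not a forecast. The primary analysis is unaffected.

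**What to change.** In the SAP, under Analysis of other secondary outcomes, state that:

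- 90-day survival for the weights is estimated separately in each arm, or equivalently with all treatment-by-covariate terms;
- the covariates are those of the SAP's adjusted death model, including baseline eGFR, plus serum creatinine and oliguria at randomisation;
- the SAP's multiple-imputation procedure, now written only for the adjusted primary analysis, also applies to missing covariates in the weight model;
- weighted baseline balance among survivors is reported by arm.

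The added variables are already in SAP Table 1, so the cost is a few lines of SAP text and of R code. The weights become slightly more variable. Balance will also be limited by how well baseline eGFR is measured: Protocol section 2.2.3 expects many patients to lack a pre-hospital creatinine, and section 2.2.2 then takes the lowest in-hospital value as baseline. The 1.000 in the tables assumes a perfectly measured factor, so in practice the correction will be incomplete. The primary analysis, the multinomial model and the composite outcome stay as they are.
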